16.3 The query process

The Monitor will review the eCRFs and evaluate them for completeness and consistency. Data in the eCRF will be compared with the respective source documents to ensure that there

are no discrepancies for critical data as described in the RBM plan. All entries, corrections, and alterations are to be made by the Investigator or designee. Neither the Monitor nor any other study team member besides site staff can enter data in the eCRF.

If corrections are needed, queries will be raised within the eCRF, either as a result of built-in edit checks or manually raised by the monitor. An appropriate member of the site staff will answer the queries in the eCRF either by correcting the data or by entering a response to the query. The monitor will either approve the answer/correction or re-issue the query.

16.4 Audit trail

All entries in the eCRF will be fully recorded in a protected audit trail. Once clinical data have been saved, corrections to the data fields will be audit trailed, meaning that the reason for change, the name of the person who made the change, together with time and date will be logged.

16.5 External data

External data consists of data that are not recorded in the eCRF. Data may be received in electronic format or as a paper printout. Key variables are defined in order to uniquely identify each sample record. File and data formats are agreed with the external data provider.

16.6 Medical coding

Medical coding will be performed by trained personnel at CTC. AEs and medical/surgical history verbatim terms will be coded using the Medical Dictionary of Regulatory Activities (MedDRA; latest version available at start of coding). Prior and concomitant medications will be coded according to the World Health Organisation (WHO) Anatomic Therapeutic Chemical (ATC) classification system. All coding will be approved by Sponsor prior to database lock.

16.7 Database lock

When all data have been entered and discrepancies solved, clean file will be declared, the database will be locked and the data will be analysed.

17 STATISTICAL METHODS AND DETERMINATION OF SAMPLE SIZE

The principal features of the statistical analysis to be performed are described in this section. A more technical and detailed elaboration of the principal features will be presented in a separate Statistical Analysis Plan (SAP), which will be signed and approved prior to database lock.

Analyses of the primary and secondary endpoints will be performed by CTC.

17.1 General

Continuous data will be presented in terms of evaluable and missing observations, arithmetic mean, SD, median, minimum and maximum value. In addition, for the parameters AUC and C_{max} the geometric mean and coefficient of variation (CV) will be presented.

Categorical data will be presented as counts and percentages. When applicable, summary data will be presented by treatment, and by assessment time. Individual subject data will be listed by subject number, treatment, and, where applicable, by assessment time.

All descriptive summaries and statistical analyses will be performed using SAS Version 9.4 or later (SAS Institute, Inc., Cary, NC).

Baseline will be defined as the visit with last data collection point prior to the first use of IP.

No imputation of missing data will be performed.

For subject questionnaires measured at each PK time point, the Bonferroni-Holm p-value adjustment will be applied.

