8 STUDY DESIGN

8.1 Overall study design and schedule of events

This will be a randomised cross-over, open-label, confinement study conducted in 24 male or female snus and cigarette consumers. The study will investigate 5 different nicotine containing products in a cross-over fashion. Cross-over in design, the study will incorporate pharmacokinetics evaluation, nicotine extraction evaluation, subjective questionnaire assessments as well as safety evaluation.

During the study participation, subjects will come for 2 visits to the clinic, including a 5-day confinement period and finally a have an end-of-study telephone call within a week of product use.

Visit 1 (Screening)

Visit 1 will take place from Day -28 to Day -1 and will include an eligibility check, review of health status and assessment of snus and cigarette consuming habits, see Table 8.1-1 for details. Subjects will be provided with smoking cessation advice and contact information for a smoking cessation support service, should they request it.

Subjects will be advised of the risks of using nicotine and referred to smoking/nicotine-use cessation support to quit if that is their intention.

Visit 2 (In-clinic treatment period, Day -1 to Day 5)

At Visit 2, subjects will be admitted to the clinic on the evening of Day -1 and will remain at the clinic until Day 5 for daily single IP use and PK, nicotine extraction, subjective questionnaire assessments and safety assessments.

On the evening of Day -1, subjects will be undertaking baseline assessments for clinical laboratory profile, vital signs and ECG. Subjects are allowed to use their own snus product until 10pm on the evening of Day -1. At 10pm, the subjects' own nicotine containing products will be collected by a member of the clinical team and returned upon completion of Day 5.

On Day -1 the subjects will also undertake a familiarisation session of the study products and questionnaires. The clinical team will explain how the products will be used and the subjects will have the opportunity to see the product and packaging. An explanation of how the questionnaires will be administered to the subjects will be given. The familiarisation session does not include a product trial and all products used in the session will not be used in the clinical study but will be retained as demonstration samples for accountability purposes.

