Baseline symptoms ⁵	11.2.12	X	X	X					
Adverse events ⁶	11.4.6				----- X -----				
Prior and concomitant medications	11.2.7				----- X -----				

BMI = Body mass index, WOCBP = women of childbearing potential, HIV = human immunodeficiency virus

1. Confirmation of eligibility criteria on Day-1 or Day 1

2. WOCBP only. Urine dipstick.

3. Clinical laboratory panel to include testing for SARS-CoV-2 (qPCR testing) on Day 5.

4. Meals (breakfast, lunch, snack, dinner and evening snack) will be served at the research clinic during Visit 2. On Day 1-5, lunch, snack, dinner and evening snack will be served approximately 4, 7, 9 and 11 hours, respectively, after start of each IP use. Breakfast will be served approximately 1 hour before start of each IP use.

5. Baseline symptoms will be recorded up until start of first use of IP on Day 1.

6. Adverse event will be recorded from start of first use of IP on Day 1.

Table 8.1-2 Detailed schedule of events for Day 1, Day 2, Day 3, Day 4 and Day 5

Assessment /time-point	Pre-IP use	Day 1, Day 2, Day 3, Day 4 and Day 5														
		00:00	00:02	00:05	00:07	00:15	00:20	00:30	00:45	01:00	01:30	02:00	04:00	06:00	08:00	12:00
Inclusion/exclusion criteria	X ¹															
Vital signs (Blood pressure and pulse)	X														X	
12-lead ECG															X ²	
Clinical laboratory profile															X ²	
PES	X ³		X ³		X ³											
MCEQ ⁴															X	
PPS															X ²	
Randomisation	X															
IP use		----- X -----													Ad lib use until 10 pm ⁵	
PK blood sampling ⁶	X	X	X	X	X	X	X	X	X	X	X	X	X	X	X	
Cotinine sampling	X												X		X	X ⁷
Nicotine pouch collection								X								
Meals ⁸		----- X -----														
Baseline symptoms ⁹	X															
Adverse events ¹⁰		----- X -----														
Prior and con meds		----- X -----														

1. Confirmation of eligibility criteria on Day-1 or Day 1.
2. Day 5 only. Clinical laboratory panel to include testing for SARS-CoV-2 on Day 5.
3. PES question 1a-g pre-use only, PES question 2a-j at timepoints 2 minutes to 4 hours, PES question 3a-y at timepoint 8 hours, PES question 4a at timepoints 30 min and 8 hours.
4. Cigarette arm only.
5. The number of units of IP used during *ad lib* use will be reported in the eCRF at the end of each treatment day.
6. PK sampling for 8 hours post-IP use on Days 1-5, respectively. Pre-use sample to be taken within 5 minutes of start of IP-use. PK sampling time windows, refer to Section 11.3.1.

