10.6 Treatment administration

In the morning of Day 1 – 5, subjects will be administered a single pouch/single cigarette as randomised. See Table 10.6-1 for instructions for use of each IP.

Following completion of the single use session and after the 8 hour PK sample, the subjects will move into an ad-lib usage period during which time they will continue to use the assigned product and no other nicotine containing products, until 10pm. The number of units of IP used during *ad lib* use will be recorded in the eCRF by the end of each treatment day.

Table 10.6-1 Investigational products – Instructions for use

Investigational product	Instructions for use
A: ZoneX #2, OND (5.8 mg nic)	A pouch of OND is to be placed between upper lip and gum, and kept still there, for 20 minutes. Oral nicotine pouches are not intended to be chewed during the usage. The IPs should not be swallowed (swallowing saliva in IP use is allowed).
B: ZoneX #3, OND (10.1 mg nic)	A pouch of OND is to be placed between upper lip and gum, and kept still there, for 20 minutes. Oral nicotine pouches are not intended to be chewed during the usage. The IPs should not be swallowed (swallowing saliva in IP use is allowed).
C: Skruf snus Fresh Slim White (10.9 mg nic)	A pouch of Skruf is to be placed between upper lip and gum, and kept still there, for 20 minutes. Oral nicotine pouches are not intended to be chewed during the usage. The IPs should not be swallowed (swallowing saliva in IP use is allowed).
D: [REDACTED]	A pouch of [REDACTED] is to be placed between upper lip and gum, and kept still there, for 20 minutes. Oral nicotine pouches are not intended to be chewed during the usage. The IPs should not be swallowed (swallowing saliva in IP use is allowed).
E: Marlboro Gold, conventional cigarette, (0.8 mg nic)	Subjects should puff approximately every 30 seconds (and should prioritise completion of PK and Questionnaires at the 2 min timepoint). Subject should aim to complete within 10 or 11 puffs and within 5 minutes but is allowed to take longer to finish the cigarette if required.

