Vital signs (systolic/diastolic blood pressure and pulse) will be summarised by sequence. Data will be presented with absolute and percent change from baseline.

All data will be listed by subject.

17.6.9 **12-lead ECG**

All ECGs will be categorised as "normal", "abnormal, not clinically significant", or "abnormal, clinically significant" (as judged by the Investigator) and summarised by sequence using frequency tables.

Changes over time will be presented using shift tables, if considered appropriate.

All data will be listed by subject.

17.6.10 **Total exposure (cotinine in plasma)**

The analysis and presentation of total nicotine exposure following plasma cotinine levels (concentration, applicable calculated PK parameters and number of *ad lib* IP units used) following controlled single use and *ad lib* use of IP will be further specified in the SAP.

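### Vital signs are summarised by sequence as change from one pre-study baseline, so the table does not show the change over each product's use

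*Protocol*

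**What the plan says.** Section 17.1 of the protocol gives one general definition: "Baseline will be defined as the visit with last data collection point prior to the first use of IP". First use falls in period 1; the footnotes to the schedules in section 8.1 state "Baseline symptoms will be recorded up until start of first use of IP on Day 1".

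Section 17.6.8 applies that definition to vital signs: "Vital signs (systolic/diastolic blood pressure and pulse) will be summarised by sequence", followed by "Data will be presented with absolute and percent change from baseline". It gives no separate baseline for each period.

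The design gives one product per day: "In the morning of Day 1 – 5, subjects will be administered a single pouch/single cigarette as randomised" (section 10.6). Section 9.9 lists five sequences, each containing all five products. Table 8.1-2, titled "Detailed schedule of events for Day 1, Day 2, Day 3, Day 4 and Day 5", marks vital signs before IP use and once late after use (read as the 8-hour column). A reading before product use is therefore planned in every period.

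Section 8.1 also uses the word baseline for an earlier reading: "On the evening of Day -1, subjects will be undertaking baseline assessments for clinical laboratory profile, vital signs and ECG".

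**The concern.** Table 7.2-1 sets a secondary objective on the tolerability and safety of each product, and lists vital-sign changes among its endpoints. A reader of the vital-sign table will want to know how blood pressure and pulse moved over the use of a given product. Two features of the plan prevent the table from showing this.

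- **Grouping.** A sequence summary pools all five products unless it is split by day. If it is split by day, each cell holds one product on one day in about five subjects.
- **Reference value.** From Day 2 onward the change is not a change over that day's product. It also contains any drift over the confinement and any lasting effect of products used on earlier days, including their ad lib use until 10 pm (section 10.6).

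The starting states differ as well. The Day 1 reading follows the subject's own snus until 10 pm and 24 hours without smoking (sections 8.1 and 9.6.1). Later mornings follow ad lib use of the previous study product, which may be the cigarette.

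The protocol treats PK differently: section 17.5.1 adjusts nicotine for the concentration immediately before each product use.

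**Working it through.** The protocol states no figure for this point, so there is none to reproduce. The inputs are 24 subjects (section 9.3), five daily periods (sections 9.9 and 10.6), vital signs before use and at 8 hours on each day (Table 8.1-2), and the baseline rule in section 17.1.

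**1. Share of subject-days affected.** Planned subject-days: 24 × 5 = 120. Days 2 to 5: 24 × 4 = 96, and 96/120 = 80%. Of 120 planned pre-use readings, the rule uses 24 as baseline and leaves 96 unused for that purpose.

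**2. Age of the baseline.** With baseline at Day 1 pre-use, its age on Day d is 24(d − 1) hours at the pre-use reading and 24(d − 1) + 8 hours at the 8-hour reading.

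| Day | Age at pre-use (h) | Age at 8-hour reading (h) | Age at 8-hour reading with same-day baseline (h) |
|---|---|---|---|
| 1 | 0 | 8 | 8 |
| 2 | 24 | 32 | 8 |
| 3 | 48 | 56 | 8 |
| 4 | 72 | 80 | 8 |
| 5 | 96 | 104 | 8 |

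On Days 2 to 5 this is 1 to 4 days at the pre-use reading and 1.3 to 4.3 days at the 8-hour reading. If the Day -1 evening reading were the baseline (assumed 20:00, with product use at 08:00), the ages would be 1.5 to 4.5 days and 1.8 to 4.8 days.

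**3. Cell size by sequence and day.** 24/5 = 4.8 subjects, all on one product, so product and day cannot be separated within a cell.

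**4. Contrasts between products.** Let B be the common baseline and Y the post-use values under products j and k. Then (Yj − B) − (Yk − B) = Yj − Yk, so B cancels. For percent change the contrast is 100(Yj − Yk)/B, where B only sets the scale.

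**5. Precision.** With equal SD σ on all days and correlation ρ between the two readings, SD(change) = σ√(2(1 − ρ)). The ratio of the fixed-baseline SD to the same-day SD is √((1 − ρ between days)/(1 − ρ same day)). The protocol gives neither correlation, so these are assumptions:

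| ρ same day | ρ between days | Ratio of SDs |
|---|---|---|
| 0.8 | 0.8 | 1.00 |
| 0.7 | 0.6 | √(0.4/0.3) = 1.15 |
| 0.8 | 0.7 | √(0.3/0.2) = 1.22 |
| 0.8 | 0.6 | √(0.4/0.2) = 1.41 |

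For scale, with an assumed σ of 10 mmHg and n = 24, the last row moves the SD from 6.3 to 8.9 mmHg and the 95% half-width of a mean change (1.96 × SD/√24) from 2.5 to 3.6 mmHg. When the two correlations are equal, nothing is lost.

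**The case against.** The case for leaving the text alone has real substance.

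- **Nothing is decided on this table.** Section 11.4.8 has the investigator judge each out-of-range value for clinical significance and report significant post-use values as adverse events. The baseline in 17.1 plays no part in that. This stands, and it limits the point to how a descriptive table is read.
- **The readings are not lost.** Section 17.6.8 lists all data by subject, and section 17.1 provides for summaries by treatment and assessment time where applicable. If day and time are shown and data are complete, the same-day mean change is the difference between two tabulated means. This is true of means. The SD, median and range of the same-day change cannot be recovered that way, and 17.6.8 specifically names sequence as the grouping.
- **A reader might infer that product comparisons are biased.** The documents do not support that. The common baseline cancels (step 4), each product occurs once in every period across the five sequences, so drift over the stay is nearly balanced, and no product contrast is planned for vital signs.
- **A reader might infer a fixed loss of precision.** That is not supported either, because the loss depends entirely on the assumed correlations and may be nil.
- **The same-day value is not clean.** It follows the previous day's ad lib use. The sequences in 9.9 are one cyclic rotation, so after period 1 each product always has the same predecessor. Only the pre-first-use value is free of study products. Meals and permitted coffee also fall between the pre-use and 8-hour readings. This is a good reason to show both changes, but not to omit the same-day one.
- **The SAP could refine the rule.** It was not available for this check. The protocol nonetheless states a rule, and a SAP that followed it literally would keep the problem.

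**Conclusion.** The point holds as a limited one. As written, sections 17.1 and 17.6.8 produce a vital-sign table that is grouped by sequence and, for 96 of 120 planned subject-days, referenced to a value 1 to 4 days old that precedes other study products. That table does not answer the per-product safety question, although the readings needed are already scheduled. Of the two defects, the grouping by sequence is the more direct obstacle; a new baseline alone would leave it in place.

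The harm is confined to a descriptive secondary safety summary. Cmax and AUCt are untouched, since their adjustment uses the sample before each use.

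The subject-day count assumes all 24 subjects complete. The 1-to-4-day figure takes the Day 1 pre-use reading as baseline. The definition does not settle that choice cleanly: it refers to a visit, and Visit 2 contains both the Day -1 evening reading and the Day 1 pre-use reading.

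**What to change.** In sections 17.1 and 17.6.8:

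1. For blood pressure and pulse, define a period baseline as the pre-use value on the same day, and summarise the change from it by product.
2. Show the change from the pre-first-use value as well, because the same-day value may carry residue from the previous day's ad lib product under the cyclic sequences.
3. Keep the single pre-first-use baseline for laboratory tests and ECG, which are not repeated daily, and label those changes as cumulative over the treatment period.
4. Where both a Day -1 evening and a Day 1 pre-use reading exist, state which one is the pre-first-use baseline, and reconcile this with the wording in section 8.1.

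No new measurement is needed. The cost is wording, programming and one additional descriptive table.

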17.2 Determination of sample size

No formal sample size calculation has been performed for this study. The proposed sample size is considered sufficient to provide adequate information for the study objectives.

Approximately 48 subjects will be screened to achieve 24 randomised subjects.

17.3 Analysis data sets

17.3.1 *Full analysis set*

The Full Analysis Set (FAS) will consist of all subjects who have been randomised and used at last one of the IPs and who has at least one post-baseline assessment of data.

17.3.2 *Safety analysis set*

The Safety Analysis Set will comprise all subjects who used at last one of the IPs.

17.3.3 *Per protocol set*

The Per Protocol Set (PPS) will consist of all subjects who have been randomised and completed the study without any major protocol deviations that are judged to compromise the analysis of the data. All protocol violations will be judged as major or minor prior to database lock.

17.3.4 *Pharmacokinetic analysis set*

The Pharmacokinetic analysis set (PKAS) will consist of all subjects who used at least one of the IPs and provided an evaluable plasma concentration profile and who have no AEs or protocol deviations judged to affect the PK analysis. Individual PK values may be excluded from the analysis as specified in the SAP. The PKAS will be used as the per protocol analysis set.

17.4 Description of study population

17.4.1 *Demographics and baseline characteristics*

Descriptive statistics for demographics, physical examinations, weight and height will be presented by sequence.

17.4.2 *Medical/surgical history and prior/concomitant medication*

Medical/surgical history will be presented by system-organ-class (SOC) and preferred term (PT). Prior/concomitant medications will be presented by ATC level 3 and 5.

Medical/surgical history and prior medications will be presented overall by descriptive statistics and listings. Concomitant medications will be presented by sequence.

All data will be listed by subject.

17.4.3 *Treatment compliance*

The number of subjects treated in sequence and their individual IP use will be listed.

17.4.4 *Heaviness of smoking index*

Scores from the individual HSI will be presented with frequency tables including number of observations and percent. The sum of the 2 questions will be presented with descriptive statistics by sequence.

17.5 Analysis of primary endpoints

17.5.1 *Analysis of pharmacokinetics*

The PK analysis will be based on the PK analysis set and performed by CTC. The PK parameters will be calculated by non-compartmental analysis (NCA) using the software Phoenix WinNonlin® version 8.1 or later (Certara, U.S.A.).

The following non-compartmental PK parameters will be determined for each IP use:

- AUC_{inf} (baseline adjusted [when possible] and non-baseline adjusted)
- AUC_t (baseline adjusted [when possible] and non-baseline adjusted)
- AUC_{0-90} (baseline adjusted [when possible] and non-baseline adjusted)
- C_{max} (baseline adjusted [when possible] and non-baseline adjusted)
- C_{last} (baseline adjusted [when possible] and non-baseline adjusted)
- T_{max} (baseline adjusted [when possible] and non-baseline adjusted)

- $T_{1/2}$ (baseline adjusted [when possible] and non-baseline adjusted)

$\text{Lambda}_{\text{az}}$ (with acceptance criteria; R^2 , extrapolated AUC) will be calculated to support baseline adjustment of above PK parameters.

C_{max} and T_{max} will be derived from the observed plasma concentration data. The AUC will be calculated using log-linear trapezoidal interpolation (linear - up, log - down). Calculations will be based on the actual sampling times recorded during the study. Concentrations below Lower limit of quantification (LLOQ) occurring before C_{max} will be treated as zero.

Concentrations below LLOQ occurring after C_{max} will be omitted from the analysis. AUC_t , and C_{max} will be corrected for and calculated with and without nicotine baseline corrections. Where plasma nicotine concentrations are above the lower limit of quantification immediately prior to product use (-5 minutes), PK parameters will be calculated from baseline adjusted concentrations using subjects' elimination rate constant.

Summary statistics for the PK parameters will be presented by product with number of measurements, arithmetic mean, SD, CV, median, minimum, maximum, geometric mean, geometric CV%. All data will be listed by subject.

The primary objective will be examined by the following statistical comparisons for AUC_t and C_{max} :

- Product A versus Product B, C, D and E, respectively
- Product B versus Product C, D and E, respectively
- Product C versus Product D and E, respectively
- Product D versus Product E

Log transformed nicotine C_{max} and AUC_t estimates will be evaluated separately in a linear mixed-effects analysis of variance model with fixed effects for period, sequence, and product, and a random effect for subject. If the assumptions for this model will be inappropriate will the fixed effects period and sequence be removed from the model. The above product differences will be back-transformed to present the ratios of geometric least squares (LS) means and 95% CIs of each test product versus each other from the same model.

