In the morning of Day 1, after pre-use assessments and confirmation of eligibility, the subjects will be randomised and then administered a single pouch/single cigarette of the IP in the sequence to which they have been randomised. Oral nicotine IP will be used for 20 minutes with standard use instructions. The cigarette will be smoked in approximately 5 minutes with puffs taken at regular intervals approximately 30 seconds apart. PK sampling will be done pre-IP use and at 2, 5, 7, 15, 20, 30, 45, 60, 90 minutes, 2, 4, 6 and 8 hours post-IP use start. Sampling for plasma cotinine levels will be taken pre-IP use and at 4, 8 and 12 hours post-IP use start. Used pouches will be collected for analysis of nicotine extraction. Questionnaires will be administered to the subject at defined intervals throughout the day. Safety will be followed throughout the day. Subjects will be allowed to use the IP, to which they are assigned that day, *ad lib* after the 8-hour timepoint until 10 pm.

In the morning of Day 2, after pre-IP use assessments, the subjects will be administered a single pouch/single cigarette of the IP in the sequence to which they have been randomised. IP will be used for 20 minutes with standard use instructions. The cigarette will be smoked in approximately 5 minutes with puffs taken at regular intervals approximately 30 seconds apart. PK sampling will be done pre-IP use and at 2, 5, 7, 15, 20, 30, 45, 60, 90 minutes, 2, 4, 6 and 8 hours post-IP use start. Sampling for plasma cotinine levels will be taken pre-IP use and at 4, 8 and 12 hours post-IP use start. Used pouches will be collected for analysis of nicotine extraction. Questionnaires will be administered to the subject at defined intervals throughout the day. Safety will be followed throughout the day. Subjects will be allowed to use the IP, to which they are assigned that day, *ad lib* after the 8-hour timepoint until 10 pm.

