9.3 Number of subjects

Twenty Four subjects will be included in the study. Approximately 48 subjects will be screened to achieve a total of 24 randomised subjects.

For replacements of subjects who discontinue from the study, see Section 9.8.

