9.8 Subject withdrawal

9.8.1 *General withdrawal criteria*

Subjects are free to discontinue their participation in the study at any time and for whatever reason without affecting their right to an appropriate follow-up investigation or their future care. If possible, the reason for withdrawal of consent should be documented.

Subjects may be discontinued from the study at any time at the discretion of the Investigator.

Reasons for discontinuation include:

- Subject decision
- Severe non-compliance to study protocol procedures, as judged by the Investigator and/or Sponsor
- Subject is lost to follow-up.
- Significant AEs posing a risk for the subject, as judged by the Investigator and/or Sponsor
- Withdrawal of informed consent to the use of biological samples
- Pregnancy
- Death
- Meeting of an exclusion criterion during the study, which, in the opinion of the Investigator, may pose a risk for the subject

9.8.2 *Procedures for discontinuation of a subject from the study*

A subject who prematurely discontinues participation in the study will always be asked about the reason(s) for discontinuation and the presence of any AEs. If a subject withdraws consent, the Investigator must ask the subject if he/she is willing, as soon as possible, to be assessed according to the procedures scheduled for the end-of-study visit. Any ongoing AEs will be followed as described in Section 11.4.6.12.

The primary reason for discontinuation/early withdrawal must be specified in the eCRF and final product accountability must be performed.

9.8.3 *Subject replacement*

Subjects who are prematurely withdrawn from the study for any reason may not be replaced during the course of the study.

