9.9 Randomisation

On Day 1, subjects will be randomised to one of 5 treatment sequences. The five different products are:

- A: ZoneX #2, OND, white tobacco-free nicotine pouch, 5.8 mg nicotine/pouch
- B: ZoneX #3, OND, white tobacco-free nicotine pouch, 10.1 mg nicotine/pouch
- C: Skruf snus fresh slim white, 10.9 mg nicotine/pouch
- D: [REDACTED]
- E: Marlboro Gold, conventional cigarette, 0.8 mg nicotine/cigarette

The 5 randomisation sequences are:

Sequence 1: A:B:C:D:E

Sequence 2: B:C:D:E:A

Sequence 3: C:D:E:A:B

Sequence 4: D:E:A:B:C

Sequence 5: E:A:B:C:D

A computer-generated randomisation list will be created by CTC using SAS Proc Plan, SAS Version 9.4. The randomisation list will contain subject number, sequence and treatment and will be kept by the randomiser until database lock. A copy of the randomisation list will be provided to the research clinic.

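### The only stated remedy for a failed primary model, dropping period and sequence, does not cure non-normal residuals or unequal variances and adds an assumption of no day effect

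*Protocol*

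**What the plan says.** Protocol Section 17.5.1 analyses log C_max and log AUC_t separately in a "linear mixed-effects analysis of variance model with fixed effects for period, sequence, and product, and a random effect for subject". The primary result is the set of ten pairwise product comparisons, reported as "ratios of geometric least squares (LS) means and 95% CIs of each test product versus each other from the same model". The next step is fixed in advance: "If the assumptions for this model will be inappropriate will the fixed effects period and sequence be removed from the model". The same sentence stands in the synopsis under Statistical methods.

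No other remedy for the primary model appears in the protocol. Wilcoxon tests are named only for extracted dose (Section 17.6.2) and the product evaluation scale (Section 17.6.3). Section 17 leaves technical detail to an SAP, which was not available for this review.

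Four design features bear on the point:

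- Section 8.1, Day -1: "Subjects are allowed to use their own snus product until 10pm on the evening of Day -1".
- Section 8.1, Days 1 to 4, after the 8-hour sample: "Subjects will be allowed to use the IP, to which they are assigned that day".
- Sections 9.3 and 9.9: "Approximately 48 subjects will be screened to achieve a total of 24 randomised subjects", and "On Day 1, subjects will be randomised to one of 5 treatment sequences".
- Section 9.8.3: "Subjects who are prematurely withdrawn from the study for any reason may not be replaced during the course of the study".

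**The concern.** The failures one normally checks for in this model are non-normal residuals and residual variances that differ by product. The second is plausible here, because one pooled variance serves four pouches and a cigarette. Removing two fixed effects touches neither. It makes the model more restrictive, since it then needs all five days to be exchangeable.

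The protocol does not support exchangeable days. Day 1 follows an evening with the subject's own snus. Days 2 to 5 follow an evening with the product assigned on the preceding day. Section 8.1 also gives 30 minutes of pouch use on Day 5, while the synopsis and Table 10.6-1 give 20. Those passages must be reconciled; as they stand, they describe another difference between days.

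Exact balance over days is not available to protect the product ratios either. Twenty-four subjects do not divide into five sequences (24/5 = 4.8), and withdrawals may go unreplaced. If the rule is triggered, the failed assumption remains. Any day effect then goes into the residual error and, where sequences are unequal, into the primary ratios.

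**Working it through.** **Inputs.** From the protocol: 24 subjects, five products over five days, the five cyclic sequences of Section 9.9, and the model and 95% CIs of Section 17.5.1. The protocol gives no variances, no period effect and no sample size calculation, so there is no figure of its own to reproduce. Assumed: within-subject log-SD σ = 0.30 (range 0.20-0.40), allocation 5/5/5/5/4, and either a trend of 5% or 10% per day or a 10-20% shift on Day 1 only. Simulations used 20,000 trials per case with complete data. In that setting sequence is absorbed by subject, and dropping it leaves the product contrasts unchanged; only the loss of period matters.

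**Step 1. Is there a parsimony reason to drop period?** There are 24 × 5 = 120 observations. Residual degrees of freedom are 120 − 24 − 4 − 4 = 88 with period and 120 − 24 − 4 = 92 without. With no true period effect, the simulated CI width ratio (without/with period) is 0.999. There is nothing to gain.

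**Step 2. Does the remedy repair the failure?** Let the pouches have log-SD 0.30 and the cigarette sE. The pooled variance is (4 × 0.09 + sE²)/5, and approximate coverage for A versus E is 2Φ(1.96 × √[2 × pooled/(0.09 + sE²)]) − 1.

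- sE = 0.45: pooled = 0.1125, ratio = 0.225/0.2925, coverage 91.4%. Simulated: 91.7% with period, 91.6% without.
- sE = 0.60: pooled = 0.144, ratio = 0.288/0.45 = 0.64, coverage 88.3%. Simulated: 88.6% with period, 88.5% without.

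For non-normal residuals (t with 3 df, or lognormal), simulated coverage is 94.9-95.2% under both models, and mean widths agree to 0.001. The remedy changes nothing in either case.

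**Step 3. Effect on CI width when a real day effect is ignored.** The period sum of squares moves into the residual, so the width ratio is about √[1 + 24 × S/(92σ²)], where S is the sum of squared deviations of the five day effects from their mean. With σ = 0.30, 92σ² = 8.28.

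| Day effect | S | 24 × S | Approximate ratio | Simulated |
|---|---|---|---|---|
| 5% per day | 10 × 0.0488² = 0.0238 | 0.571 | 1.034 | 1.032 |
| 10% per day | 10 × 0.0953² = 0.0908 | 2.18 | 1.124 | 1.122 |
| Day 1 only, 10% | 0.8 × 0.0953² = 0.0073 | 0.174 | 1.010 | about 1% wider |
| Day 1 only, 20% | 0.8 × 0.1823² = 0.0266 | 0.638 | 1.038 | about 4% wider |

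Over σ = 0.20-0.40 the widening is 2-7% for 5% per day and 7-26% for 10% per day. At σ = 0.30, coverage without period rises to 95.4-95.9% and 96.9-97.4% respectively.

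**Step 4. Bias.** Bias equals the log trend times the difference in mean day between two products.

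- At 5/5/5/5/4 the largest is D versus E. The day totals are 70 and 74, so bias = 4/24 × 0.0953 = 0.016 log units. For scale, the planned 95% CI is about 0.343 log units wide in full.
- At an illustrative 8/6/4/3/3 split the day totals are A 69, B 63 and E 85. A versus E: 16/24 × 0.0953 = 0.064, simulated coverage 92.7%. B versus E: 22/24 × 0.0953 = 0.087, simulated coverage 88.2%. With period kept, all contrasts cover at about 95%.
- With 2 to 4 random unreplaced drop-outs and a trend of 0.1 log units per day (2,000 random patterns for each number), the worst-contrast bias has median 0.027-0.030 and maximum 0.055-0.077.

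**The case against.** **The trigger need not mean residuals.** The protocol does not say which assumptions it has in mind. If the worry is thin sequences after exclusions, simplifying the fixed part is a coherent step. That would justify dropping sequence, which is harmless, but not period. If the worry is a period effect that differs by product, removing period does not repair that either. No reading makes the rule a sound general remedy.

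**Much of the previous-evening effect is carry-over.** In the cyclic sequences each product has the same predecessor on Days 2 to 5 (A after E, B after A, and so on). That influence is aliased with product, and a period term cannot remove it. Overnight abstention and baseline-adjusted parameters shrink it further. This stands and limits what period adjustment achieves. The switch from own snus before Day 1 to a study product afterwards is still a Day 1 difference, and its common part is absorbed by period.

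**The large figures need strong assumptions.** A rise of 10% on each day is about 46% from Day 1 to Day 5 (1.10⁴ = 1.46), and the 8/6/4/3/3 split is invented. A Day 1 shift of 20% alone gives a bias of only 1/24 × 0.1823 = 0.008 log units at 5/5/5/5/4. This stands: the cases in between are the more likely ones.

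**Under-coverage from unequal variance is not caused by this sentence.** True: it is the same with and without period. It is shown only because the stated remedy leaves it untouched.

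**An SAP could add better remedies.** It could, but the protocol already fixes the action, so this is not a detail merely left open.

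**Conclusion.** The concern holds. The fixed remedy does not match the failures it would normally answer, and it removes an adjustment that the design calls for.

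The size is modest. Near balance the consequence is wider, conservative intervals: about 3% for an assumed 5% per day, 12% for 10% per day and 1-4% for a shift on Day 1 alone, with bias of at most 0.016 log units in these cases. It becomes bias with under-coverage only when sequences are clearly unequal and the trend is strong. All of this rests on assumed log-SDs, trends and allocations, because the protocol gives none. The study has no success threshold that depends on the rule, and the rule acts only if triggered. It should still be corrected, because the affected ratios are the primary result and keeping period costs almost nothing.

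**What to change.** Delete the sentence in Section 17.5.1 and in the synopsis. Keep period, product and the random subject effect in the primary model in all cases; sequence may stay or go. Replace the sentence with, for example:

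> If residual variances differ by product, the same model is refitted with product-specific residual variances. If residuals are clearly non-normal, a rank-based or bootstrap sensitivity analysis is reported beside the primary result.

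The SAP can set the diagnostic criteria and choose between the rank-based and bootstrap method.

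The cost is one sentence in two places and a few lines of code, with no extra data. If there is truly no period effect, keeping period spends 4 degrees of freedom (88 instead of 92) and widens the CIs by about 0.1% at 5/5/5/5/4, or about 2% at 8/6/4/3/3. Keeping period does not remove carry-over between consecutive products, so it should not be presented as doing so.
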